**REVISION CHRONOLOGY:**

Version Date	Document Type	Change(s) since last version
10-16-2017	Original	n/a
2-22-2018	Amendment 01	Revisions: 
 
1. Added statement regarding the data captured from devices being for research use only
 
2. Updates subject identification to include study provider referral
 
3. Added collection of height and weight at Visit 1
 

		4. Added details regarding the 2 step process for full data integration
--	--	---

Description: PPD [redacted] sensor pilot  
Unique Identifier: HO-17-17827 / 207223

**Investigator Protocol Agreement Page**

- I confirm agreement to conduct the study in compliance with the protocol.
- I acknowledge that I am responsible for overall study conduct. I agree to personally conduct or supervise the described clinical study.
- I agree to ensure that all associates, colleagues and employees assisting in the conduct of the study are informed about their obligations. Mechanisms are in place to ensure that site staff receives the appropriate information throughout the study.

Investigator Name: [name] PhD

PPD

*[name]*

*20-Mar-2018*  
Date (DD-MMM-YYYY)

PROTOCOL SYNOPSIS

Unique Identifier	HO-17-17827 / 207223
Abbreviated Title	PPD Sensor Pilot
Rationale	This is a pilot study exploring the opportunity for accessing data directly from electronic health records (EHR) and integrating with data from various sensors and mobile devices. The goal is to assess how to scale these methods for use in interventional trials.
Objectives (Primary, Secondary)	
 
• To assess how the use of EHR may be beneficial in recruiting populations for future clinical trials,
 
• To evaluate how representative the consented, study population is when compared to the eligible population,
 
• To develop a monitoring dashboard for integration of data from various sources,
 
• To evaluate patient experience, data quality and consistency with novel, patient-data collection methods:             
 
○ Mobile spirometry
 
○ Sensor for monitoring rescue medication use
 
○ Sensor for monitoring maintenance medication use
 
○ Physical activity monitor
 
○ Electronic patient reported outcomes (ePROs)
 
 
 
• To assess the relationships between EHR-based healthcare utilization (ambulatory care visits and hospitalizations for COPD or asthma exacerbations) and lab measures (specified below) with patient data remotely collected via methods outlined in previous bullet.
 

Study Design	A prospective study that will include two cohorts of patients (COPD and asthma) identified via EHR database analyses recruited from sites of usual care. Participants will attend two visits at 0 and 6 months and data will be collected via sensors and mobile devices between the visits.
Study Population and Sampling Methods	
Eligibility Criteria Inclusion Criteria All patients will be selected based on the following criteria.
 
Inclusion Criteria for COPD cohort: To be eligible to participate in this study, a subject must meet all of the following criteria:
 
 
• Provide signed and dated informed consent form.
 
• Be willing to comply with all study procedures and be available for the duration of the study.
 
• Age ≥ 40
 

- Diagnosed with COPD, defined as COPD listed on the patient's problem list and one of the following:
  - At least one inpatient hospitalization with a COPD diagnosis listed as the primary or secondary diagnosis (J41.x, J42.x, J44.x [chronic bronchitis], J43.9 [emphysema] or J44.9 [Chronic obstructive pulmonary disease, unspecified]) in the last 12 months OR
  - At least one emergency room encounter with a COPD diagnosis (J41.x, J42.x, J44.x, J43.9, J44.9) listed as the primary or secondary diagnosis in the last 12 months OR
  - At least two encounters of any combination of the following (each must be a distinctly different event with different dates of service):
    - an outpatient encounter with a diagnosis of COPD exacerbation (J44.1), Acute bronchitis (J20.x), or bronchitis (J40) listed as the primary or secondary diagnosis in the last 12 months, OR
    - an urgent care encounter with a COPD diagnosis (J41.x, J42.x, J44.x, J43.9, J44.9) listed as the primary or secondary diagnosis in the last 12 months
- At least one order for an inhaled COPD medication during the prior year.
- 12+ months of data available in the integrated EHR data prior to date of screening.

**Inclusion Criteria for Asthma cohort**

- Provide signed and dated informed consent form.
- Be willing to comply with all study procedures and be available for the duration of the study.
- Age ≥ 18
- Diagnosed with asthma, defined as asthma listed on the patient's problem list and one of the following:
  - At least one inpatient hospitalization with an asthma diagnosis (J45.x) listed as the primary or secondary diagnosis in the last 12 months OR
  - At least one emergency room encounter with an asthma diagnosis (J45.x) listed as the primary or secondary diagnosis in the last 12 months OR
  - At least two urgent care encounters, with different dates of service, with an asthma diagnosis (J45.x)

	
listed as the primary or secondary diagnosis in the last 12 months OR
 
 
○ At least three or more prescriptions or prescription refills in the past 12 months for any combination of the following: an inhaled glucocorticoid with or without a second controller (Montelukast, Theophylline, a long-acting beta agonist [LABA] alone), or a combination drug with a LABA and an inhaled glucocorticoid
 
● 12+ months of data available in the integrated EHR data prior to date of screening
 
 
Exclusion Criteria (screening question) for COPD cohort
 
 
● Inability/Unwillingness to use the required devices, or
 
● Inability to read and understand English
 
 
Exclusion Criteria (screening question) for Asthma cohort
 
 
● Inability/Unwillingness to use the required devices, or
 
● Inability to read and understand English, or
 
● Diagnosis of COPD listed on problem list
 

Data Source	
Integrated EHR records (primary and specialty care) are the key source for retrospective analysis and for identifying patients. Digital data collection from patient reports, devices, and sensors over six months are the key source for the prospective analysis. The full data integration will be accomplished in two stages.

Data Analysis Methods	
 
● Spirometry 
 
○ Change from baseline in FEV1
 
 
 
● Activity 
 
○ Median/mean steps per day
 
○ Median/mean daily activity level based on vector magnitude units (VMUs)
 
 
 
● PROactive total score and difficulty domain score (C-PPAC)
 
● E-RS:COPD symptoms Exacerbations (COPD cohort only) 
 
○ EXACT-defined events
 
 
 
● HCRU 
 
○ Median/mean number of primary care visits for COPD/asthma conditions
 
○ Median/mean number of secondary care visits (inpatient, urgent care and ED visits) for COPD/asthma conditions
 
○ Median/mean number of all primary care visits
 
○ Median/mean number of all secondary (inpatient, urgent care and ED visits) care visits
 
 
 

	
 
○ Summary of new prescriptions for any COPD/asthma treatments
 
○ Number of days in hospital for COPD/asthma
 
○ Number of albuterol inhalers (adjusted to equivalence of 200 actuations) prescribed
 
● ePRO 
 
○ Mean change from baseline in CAT (COPD cohort)
 
○ Mean change from baseline in ACT (asthma cohort)
 
 
 
 
All PRO data will be collected via electronic platform  Further details and exploratory analyses describing patterns of cohort and individual changes will be described in the full statistical and analysis plan.  All analyses will be performed using SAS v9.4 (SAS Institute, Inc., Cary, NC, USA). These will be described in more detail in the full statistical analysis plan.

Sample Size and Power	
This study aims to evaluate the patient experience with new data collection methods and the association between new methods and the EHR-defined variables regarding disease severity and healthcare resource utilization, therefore no comparisons or hypothesis testing will be performed. In order to collect adequate information about the feasibility of these new data collection methods, approximately 200 PPD [redacted] patients from the integrated delivery network (IDN) will participate in the study (100 in each group COPD and asthma). If we assume a dropout rate of at most 25%, we will have complete data on at least 150 patients, which will be sufficient to address feasibility of the new collection methods in two different cohorts. In addition, since this is a pilot study to assess feasibility of an interventional study that would use the data capture methods, a formal power calculation is not required.

Limitations	
Participants included in this study will be selected from among those within the PPD [redacted] IDN, therefore may not be representative of a sample of all COPD and asthma patients from the US. There will likely be a selection bias based on which patients are willing to participate in a study with multiple devices and due to established inclusion/exclusion criteria. Medication use and activity will be monitored using sensors so there is a risk that the patient's behavior may be altered.

## ABBREVIATIONS

ACT	Asthma Control Test
AE	Adverse event
CAT	COPD Assessment Test
COPD	Chronic obstructive pulmonary disease
EHR	Electronic Health Records
ERS-COPD	Evaluating Respiratory Symptoms in COPD
ePROs	Electronic patient reported outcomes
PPD	PPD
IDN	Integrated Delivery Network
IRB	Institutional Review Board
PACDC	Phenomic Analytics Clinical Data Core
VMUs	vector magnitude units

## 1 INTRODUCTION/BACKGROUND

Electronic health records (EHR) are becoming more common in clinical practice in the United States. This study aims to assess the feasibility of collecting increasing amounts of clinical study data from patients (e.g. sensor and web/app based methods) and their EHR to facilitate more efficient and meaningful research with acceptable quality.

## 2 OBJECTIVES

### 2.1 General Objective

To recruit small cohorts (n=100 each) of chronic obstructive pulmonary disease (COPD) and asthma patients from their usual healthcare environment to gain experience with novel, digital data collection methods combined with EHR extraction to explore feasibility of larger real-world studies. Overall, we hope to assess how the use of EHR may be beneficial in recruiting populations for future clinical trials.

### 2.2 Specific Objectives

- To evaluate how representative the consented, study population is when compared to the eligible population.
- To develop a monitoring dashboard for integration of data from various devices
- To evaluate patient experience, data quality and consistency with novel, patient-data collection methods:
  - Mobile spirometry
  - Sensor for monitoring rescue medication use
  - Sensor for monitoring maintenance medication use
  - Physical activity monitor
  - Electronic patient reported outcomes (ePROs) – monthly CAT (COPD cohort), ACT (asthma cohort)
    - monthly PROactive – using the C-PPAC
    - For COPD only: EXACT PRO daily symptoms [ERS-COPD]
- To assess the relationships between EHR-based healthcare utilization (ambulatory care visits and hospitalizations for COPD or asthma exacerbations) and lab measures (specified below) with patient data remotely collected via methods outlined in previous bullet, for example.
  - EHR spirometry
  - Blood WBC, eosinophils, neutrophils (number and %)
  - Other blood biomarker samples if available (e.g. fibrinogen, CRP, periostin, sRAGE etc)

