## 3 RESEARCH METHODOLOGY

### 3.1 Study Design

This is a prospective study that will include two cohorts of patients (COPD and asthma) identified via EHR database analyses, study provider referral (COPD and asthma diagnoses with and without specialist confirmation), or recruited from sites of usual care. Participants will attend two visits with study team members at 0 and approximately 6 months, as most data will be captured either remotely via sensors and devices provided by GSK to the patients or via a data pull of EHR data. At the baseline visit, study team members will obtain written informed consent, distribute study devices, and provide instruction for proper use of study devices and platforms. Approximately six months later, at the second visit, the patient will return study devices. Patients will then be called to complete an exit interview to provide relevant feedback on the study.

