### **3.3 Study Visits**

#### **3.3.1 Recruitment**

The study team will utilize three recruitment methods. The first method is to have a Phenomic Analytics Clinical Data Core (PACDC) data broker identify potential participants through a data pull of EHR data or by review of PPD clinical dashboard. The second method is for study providers to refer eligible patients to the study team. The third method will have a study team member review the pulmonary clinics schedules and identify eligible patients. Potential subjects will be invited to participate.

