### **3.5 Data Source / Data Collection**

Integrated EHR records (primary and specialty care) are the key source for retrospective analysis and for identifying patients. Digital data collection from patient reports, devices, sensors, and EHR records over six months are the key sources for the prospective analysis. The full data integration will happen in two stages and a summary of variables to be extracted in each stage is included in Section 6.4. The study database will be housed on a third-party vendor's secure network. In the initial data integration stage and at the baseline visit, the study

team member will manually enter patient information (including name, MRN, date of birth, gender, ethnicity, date of consent, height, and weight) into the study portal built into the study tablet. The information entered into the study portal will calibrate the predictive formulas in the study devices and flow to the study database on the third-party vendor's secure network. Patients will then take the study devices home and use them as instructed. Data from the study devices, including the mobile spirometry device, the sensors for rescue and maintenance medications, activity monitors, and the ePRO platform will flow directly to the database on Vendor A's network. During stage one of the data integration, no EPIC data will be sent to the study database on the third-party vendor's secure network.

During stage two of the data integration, EHR data will be extracted and combined with device data in the database housed on Vendor A's network. Vendor A will de-identify the study database and send the data set to Vendor B. PPD staff will administer a study Exit Interview at the follow-up visit asking participants to provide feedback on the study, the study devices, and ePRO platform.

PPD data is part of the mini-sentinel monitoring system which means their data set meets standard criteria for data integrity and quality.

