### 6.4 Personally Identifiable Information (PII)

The final data set will be de-identified and will not contain PHI. However, Vendor A will have access to participant names, dates, date of birth, and MRNs to integrate data from multiple data sources including study device data, ePRO, EHR data, and Exit Interview transcripts. Vendor A will remove PHI elements from the dataset. PHI accessed for recruitment will only be seen by PPD staff. The final data set, housed by Vendor B, will be de-identified.

The data in the table below, including relevant dates, will be collected. The table also outlines who will have access to each type of data during each stage of data integration.

Stage One – Data Integration				
	PPD	GSK	Vendor A	Vendor B
Names	X		X	
Medical record number	X		X	
Telephone number	X			
Date of birth/date of death	X		X	
Height and weight	X	X	X	X
Information relevant to all encounters, admissions/discharges, clinical procedures, medications administered, problem list entries, and lab values	X			
Baseline demographic variables of patients (age, sex, ethnicity, tobacco use, comorbidities)	X		X	
Clinical outcomes and procedural related complications	X			
Information from study devices, sensors, and electronic platforms	X	X	X	X
Information gather from patient interviews at study visits	X	X	X	X

Stage Two – Data integration				
	PPD	GSK	Vendor A	Vendor B
Names	X		X	

Medical record number	X		X	
Telephone number	X			
Date of birth/date of death	X		X	
Height/ Weight	X	X	X	X
Information relevant to all encounters, admissions/discharges, clinical procedures, medications administered, problem list entries, and lab values	X	X	X	X
Baseline demographic variables of patients (age, sex, ethnicity, tobacco use, comorbidities)	X	X	X	X
Clinical outcomes and procedural related complications	X	X	X	X
Information from study devices, sensors, and electronic platforms	X	X	X	X
Information gather from patient interviews at study visits	X	X	X	X

Records of data generated in the course of the study shall be retained for at least 6 years and could be used for future research studies submitted and approved by the IRB.

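### Can the plan compare consented with eligible patients when it describes no data route for eligible patients who decline, and the synopsis and body differ on recruitment?

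*Combined protocol and SAP*

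**What the plan says.** The objective, "To evaluate how representative the consented, study population is when compared to the eligible population", stands in the synopsis and in Section 2.2 of the current protocol.

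**How patients are found.** The synopsis (Study Design) describes "two cohorts of patients (COPD and asthma) identified via EHR database analyses recruited from sites of usual care". Section 3.1 describes cohorts "identified via EHR database analyses, study provider referral (COPD and asthma diagnoses with and without specialist confirmation), or recruited from sites of usual care". Section 3.3.1 lists three methods: an EHR pull or dashboard review by a data broker, referral by study providers, and a last one: "The third method will have a study team member review the pulmonary clinics schedules and identify eligible patients". Section 3.2.1.1 applies the EHR criteria to every patient, however found.

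**Where the data go.** Section 3.5 opens with "Integrated EHR records (primary and specialty care) are the key source for retrospective analysis and for identifying patients". It later says of stage two that "EHR data will be extracted and combined with device data in the database". Section 6.4 adds that "Vendor A will have access to participant names, dates, date of birth, and MRNs to integrate data from multiple data sources", and that "PHI accessed for recruitment will only be seen by PPD staff".

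**Permission and analysis.** Section 8.1 asks for a partial HIPAA waiver so that patients can be screened in advance and approached. Section 3.7 rules out comparisons and hypothesis tests. Section 4 lists descriptive summaries and Spearman correlations, and leaves detail to a full SAP that is not among the documents reviewed.

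**The concern.** A comparison with the eligible population needs baseline data on eligible patients who did not enrol. The extract described in most detail is joined to device data, which non-participants do not have. The access tables in Section 6.4 have no row for such patients or for a screening log, and the waiver request does not mention analysis of their records. Signed consent is also an inclusion criterion in both cohorts, so on a literal reading an eligible non-consenter cannot exist.

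The recruitment text adds a second doubt. If some patients come from pulmonary clinic schedules or referral, a difference from the EHR-wide pool could reflect where patients were found as well as who agreed. Section 5 names restriction to one delivery network and willingness to use devices as limits, but not the clinic route. At stake would be an objective with no route to a result, or a sampling effect misread as reluctance to use devices.

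**Working it through.** **The plan's own figure.** Section 3.7 assumes at most 25% dropout from 200 enrolled: 200 × (1 − 0.25) = 150, or 75 per cohort if dropout is equal. This matches the stated 150. Nothing in the concern bears on it.

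**Is there a route to the comparator?**

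1. Section 3.5 separates a retrospective analysis, with EHR records as key source, from the six-month prospective analysis. The sentence about combining EHR with device data describes stage-two integration. It does not say that every EHR analysis must run on the combined file.
2. Section 3.3.1 has a data broker query the EHR for potential participants, which yields a candidate pool.
3. Section 6.4 keeps recruitment information with site staff. That bars sending identifiable records of non-participants onward. It does not bar an aggregate table.

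An aggregate comparison by site staff is therefore compatible with all three sections, although none describes it.

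**Is the denominator defined?** Taking consent as part of eligibility would make the objective empty. The workable reading is patients who meet the EHR-ascertainable criteria before consent, and Section 3.2.1.1 supports it.

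**Does the mix of routes spoil the comparison?** Write the total difference as

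consented − eligible = (approached − eligible) + (consented − approached).

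The objective asks for the left side. Recruitment route enters the first term on the right and is part of the answer. Separating the two terms is a further question that the objective does not pose.

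**How large could the first term be?** Let q be the share of a cohort recruited from clinic schedules and s the clinic share of the eligible pool. Both are assumed, because the documents give neither. Suppose the other routes mirror the pool and consent is unrelated to clinic attendance. Then the participants' clinic share is P = (1 − q)s + q, and the gap is P − s = q(1 − s). With n = 100 per cohort (Section 3.4.2) and the pool share taken as known, the 95% half-width is 1.96 × √(P(1 − P)/100).

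| q | s | P | Gap | Half-width |
|---|---|---|---|---|
| 1/3 | 0.10 | 0.400 | 0.300 | 0.096 |
| 1/3 | 0.30 | 0.533 | 0.233 | 0.098 |
| 1/3 | 0.50 | 0.667 | 0.167 | 0.092 |
| 0.10 | 0.10 | 0.190 | 0.090 | 0.077 |
| 0.10 | 0.30 | 0.370 | 0.070 | 0.095 |
| 0.10 | 0.50 | 0.550 | 0.050 | 0.098 |

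The gap clearly exceeds chance error only when the clinic route is substantial. The table concerns clinic attendance alone. It shows no effect on age, sex, ethnicity, tobacco use or comorbidities, the baseline variables named in Section 6.4.

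**The synopsis.** Amendment 01 records the addition of provider referral. Section 3.1 was updated and the synopsis was not. The eligibility criteria are the same whichever text is read.

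**The case for a change.** The strongest reply is that a later SAP can define the statistic but cannot widen a waiver request, nor recover contact, decline and route counts that were not kept during recruitment. The synopsis also lists, as an aim of its own, learning how EHR use helps recruitment. That is hard to describe without knowing which participants came by the EHR pull: if a share p did, crediting all enrolment to it overstates its yield by 1/p, which is 1.5 times at an assumed p of 0.67.

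Part of this stands. The documents do not name the comparator table, its author or a route log, and a record of each participant's route would be useful. But they do not say that such records will be discarded, and no passage credits all enrolment to the EHR pull. The 1/p figure is an identity applied to an assumed share.

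On permission, Section 8.1 is one sentence summarising a request to the IRB. The application and any waiver granted are not available here, so whether an aggregate table needs more than was asked cannot be settled from these documents. That is an open question, not a demonstrated shortfall.

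**Conclusion.** No change to the plan follows. The missing denominator, variables, summary statistic and table author are details that a competent analyst would supply in the SAP: a pre-consent pool meeting the EHR criteria, tabulated by site staff and compared descriptively within each cohort. The ban on comparisons in Section 3.7 sits beside hypothesis testing and does not prevent a descriptive contrast. The synopsis wording is a clerical lag behind the amendment and alters no eligibility rule.

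No stated rule or number is shown to give a wrong result, and the 150 completers are unaffected. The possible shift in clinic share, 5 to 30 points across the cases shown, rests on assumed inputs except for n = 100, and it belongs to the difference the objective asks about. The conclusion assumes that site staff may produce an aggregate table under the permissions actually obtained. It also assumes that readers do not put the whole difference down to willingness to use devices.
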